**Prospective:**

- The study population for the prospective aspect will include recruited newborns with untreated unilateral incomplete cleft lip. Patients whose clefts are associated with a syndrome will be excluded. DynaCleft® + Nasal Elevator therapy will be discussed with parent(s) as a presurgical orthopedic option while awaiting primary cleft lip surgical repair that typically occurs between the ages of 3 to 6 months. Informed consent for participation in the study must be obtained from the patients' parents.
- Study duration will be up to three months of presurgical intervention (similar to the existing nasoalveolar molding NAM appliance protocols).
- Patients will be recruited by the Texas Cleft-Craniofacial team. ○ Infants that match the inclusion criteria will be invited to participate in this study.
- Photographs are to be taken at initial visit prior to presurgical intervention and later at completion of the DynaCleft® therapy immediately prior to lip surgery. Angles to be pictured are to include the standard anterior-posterior, profile, and worms-eye view.
- Linear measurements will be obtained with a ruler and registered in millimeters. A goniometer will be used to measure angles.
- The parents of infants enrolled in the DynaCleft® study will be asked to complete an Infant and New Parent Quality of Life survey at the initial and final visits. Components from this survey were adopted from the Infant and Toddler Quality of Life Questionnaire and the CDC Breastfeeding and Infant Practices Questionnaire (see attachments).

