**NCT04455035**

**Version Date: 07/16/2020**

**Protocol Title:** DynaCleft® Effects on Soft Tissues and on Quality of Life for Incomplete Unilateral Cleft Lip Infants

**Principal Investigator:** [name], D.D.S.

**Co-Investigators:** [name], D.D.S., Ph.D. and [name].

**Study Coordinator:** [name] and [name]

**Population:** Prospective study of 10 infants with non-syndromic unilateral incomplete cleft lip; retrospective chart review of infants with non-syndromic unilateral incomplete cleft lip without any presurgical interventions

**Number of Sites:** University of Texas Health Science Center at Houston (UTHealth) Advanced Education in Pediatric Dentistry and UTHealth Texas Cleft-Craniofacial Clinic

**Study Duration:** Two Years

**Subject Duration:** Prospective study – four months

---

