### **Retrospective:**

- The control group for this study will be obtained from a retrospective chart review of electronic health records of patients with incomplete cleft lip who underwent surgery without any presurgical interventions. These records will be obtained from the Texas Cleft-Craniofacial Team. Only records of infants with non-syndromic unilateral incomplete cleft lip will be qualified for this study. To eliminate variability, only patients treated by one pediatric plastic surgeon ([name]) will be included. All patients with complete cleft lip, or diagnosed with a syndrome, or had any surgeries not provided by the same plastic surgeon (prior to the initial cheiloplasty) will be excluded. Any records with incomplete data or necessary photographs will also be excluded.

IRB NUMBER: HSC-DB-20-0311

- Necessary photographs are to include those taken at the initial visit soon after birth and those at the visit immediately prior to lip surgery. Photographs need to include those taken in the standard anterior-posterior view, profile view, and worms-eye view.
- Linear measurements will be obtained with a ruler and registered in millimeters. A goniometer will be used to measure angles.

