**Retrospective:**

- The Texas Cleft-Craniofacial Team photo database will be queried for patients with incomplete unilateral cleft lip who have undergone cleft lip repair from 2015-2020.
  - Inclusion criteria
    - Unilateral cleft lip with or without cleft palate
    - Patients of a single surgeon ([name])
    - Patients with complete photographs: □ After birth, first visit

IRB NUMBER: HSC-DB-20-0311

- At cleft lip repair (3-4 months)
- Post-operative cleft repair (about 1 year of age)
  - Exclusion criteria
    - Bilateral cleft lip or complete unilateral cleft lip
    - Patients operated on by other primary surgeons
- Patients with incomplete photo records will be evaluated to determine if the patient should be excluded

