**Prospective:**

- One evaluator will obtain all photographs to be evaluated in this study, examine Electronic Health Records, and collect necessary data and measurements onto a password protected Microsoft Excel Spreadsheet. Measurements to be recorded may include columellar angles, nostril width, nostril height, width of the lip cleft, etc. While most of the information can be gathered directly from the photographs, some factors may require calculations such as soft tissue ratios if need be. The primary investigator will be blinded to whether or not subject has participated in the DynaCleft® study. Data are to be measured twice and results compared to account for accuracy. Participants are identified on the spreadsheet solely by an assigned code. Factors to be recorded will also include general biographical and physical information (age, gender, weight, etc.), duration of treatment and compliance of caregivers.
- Interaction with

IRB NUMBER: HSC-DB-20-0311

participants in the DynaCleft® study will involve one monthly visit up until date of surgery, usually between 3 to 6 months of age. Each appointment is estimated to be

an hour long to allow for assessment of the orthopedic, recording of information, and addressment of any concerns. The initial and last visits may require more time due to obtainment of necessary photographs. Participants will be required to receive DynaCleft® treatment for at least 2 months before lip surgery to qualify. Additionally, parents of infants with incomplete unilateral cleft lip that choose not to use the DynaCleft® + Nasal Elevator system but are willing to complete the infant quality of life assessment at time of surgery will be allowed to complete the survey. All images obtained in this study will be stored in a password protected and encrypted computer. Prospective patient images will be stored in the Electronic Health Record. Images will be de-identified.

- Parents will be asked to complete the Infant and New Parent Quality of Life questionnaire at both the initial visit and date of surgery.

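### The stated timing of lip repair differs between controls (3-4 months) and treated infants (3-6 months), treatment and participation limits do not fit the later repairs, and the analysis uses neither age nor interval.

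*Combined protocol and SAP*

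**What the plan says.** **Anchor event.** Outcome Measures sets the time points of all four primary outcomes as the initial examination and surgery, with no age window. Study Design asks for control photographs "taken at the initial visit soon after birth and those at the visit immediately prior to lip surgery". For treated infants the second photograph is taken "later at completion of the DynaCleft® therapy immediately prior to lip surgery".

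**Timing of repair.** Study Population, Retrospective, lists the required control photograph as "At cleft lip repair (3-4 months"). For treated infants, Study Design, Prospective, says that repair "typically occurs between the ages of 3 to 6 months". Study Procedures, Prospective, has monthly visits until surgery, "usually between 3 to 6 months of age".

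**Length of treatment and participation.** Study Design, Prospective, which recruits newborns, says "Study duration will be up to three months of presurgical intervention". The title page gives the subject duration as "Prospective study – four months". Study Procedures, Prospective, requires treatment for "at least 2 months before lip surgery to qualify".

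**Analysis.** The Statistics section plans a paired t-test within patients and a between-group test chosen according to the distribution of the data, at the 0.05 level. It mentions neither age nor the interval between photographs. Study Procedures lists age and duration of treatment among the items to record, without saying at which photograph age is taken.

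**The concern.** Nostril width, nostril height and cleft-lip width are linear dimensions of a growing face, recorded in millimetres; the columellar angle is the fourth primary outcome. Each is analysed as a change between two photographs. If treated infants are photographed at a different age from controls, or over a different interval, part of the difference in change reflects elapsed time and not the device. The controls are historical and there is no randomisation, so nothing in the design balances timing, and the planned test does not correct for it.

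The limits on treatment and participation add to this. Where surgery is late they conflict with treatment and visits that run up to surgery, so the text does not settle how long a treated infant is treated or followed.

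**Working it through.** The plan states no effect size, SD, power or control-group size, so it has no figure of its own to reproduce. The check has three parts.

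**1. Age at the second photograph.** Inputs: controls 3-4 months (Study Population, Retrospective); treated infants 3-6 months (Study Design and Study Procedures, Prospective). The control entry does not print the word age, but the next item in the same list, at about 1 year of age, shows that ages are meant.

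- Largest difference consistent with the ranges: 6 − 3 = 3 months.
- Midpoints: (3 + 4)/2 = 3.5 and (3 + 6)/2 = 4.5, a difference of 1 month.

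**2. Fit of the limits to treatment up to surgery.** Interval = age at surgery − age at start.

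| Age at surgery | Interval if started at birth | Earliest start within a 3-month limit | Earliest entry within a 4-month duration |
|---|---|---|---|
| 3 months | 3 months | birth | birth |
| 4 months | 4 months | 1 month | birth |
| 5 months | 5 months | 2 months | 1 month |
| 6 months | 6 months | 3 months | 2 months |

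Surgery at 3 months fits both limits. Surgery at 5 or 6 months fits them only if the infant starts well after the newborn period. With the two-month minimum in Study Procedures, the stated figures allow treated intervals anywhere from 2 to 6 months.

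**3. Illustrative size.** Assumptions: no device effect; growth moves an endpoint by 0.1-0.3 SD per month; mean age gap 1 month (the midpoints); 20 controls; two-sided t-test at 0.05. From the plan: 10 treated infants and the 0.05 level.

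Bias b = growth per month × gap, which is 0.1-0.3 SD for 1 month. The noncentrality parameter is δ = b / √(1/10 + 1/20) = b / 0.387, with 10 + 20 − 2 = 28 degrees of freedom and critical value 2.048. The false-positive rate is P(|T| > 2.048) for noncentral t with parameter δ.

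| b (SD) | δ | False-positive rate |
|---|---|---|
| 0.1 | 0.258 | 5.7% |
| 0.2 | 0.516 | 7.9% |
| 0.3 | 0.775 | 11.6% |

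At b = 0.3 SD, 10 controls give 9.7% and 40 controls give 13.2%. A mean gap of 2 months at the fastest assumed growth (b = 0.6 SD, 20 controls) gives 32.2%, but the midpoints of the printed ranges do not support a mean gap that large.

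**The case against.** The strongest reply is that the plan already has a common definition. Outcome Measures and both arms of Study Design place the second photograph at, or just before, surgery. That stands: the anchor event is shared. What is not shared is the stated age at that event, and the interval is not controlled.

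A second reply is that the figures measure different things: three months is treatment length, four months is participation, and 3-4 and 3-6 months describe when repair happens. That also stands. Three months of treatment within four months of participation is no contradiction, and a reader who takes all four figures as rival values of one quantity would be wrong. The two conflicts that remain are 3-4 against 3-6 months, and the limits against treatment of newborns until a late repair.

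A reader might also infer a period off the device before the final photograph, with relapse. The documents do not support this. Background Information has parents replacing the tape until surgery, Study Design treats completion of therapy and the eve of surgery as one occasion, and visits continue to surgery. No passage schedules a gap, and relapse is not mentioned.

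Finally, the real ages may be similar. The 3-6 month range is hedged as typical or usual, Background Information gives it as the general range for lip repair, and no passage excludes a control repaired at 5 months. This is fair: the text allows a difference in age but does not establish one.

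**Conclusion.** The concern holds in a limited form. The protocol gives different timing of repair for the two groups. Its treatment and participation limits do not fit newborns treated until surgery at 5-6 months. Its between-group comparison uses neither age nor interval. Followed as written, the plan could attribute growth to the device or let growth hide a device effect.

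The direction depends on the endpoint. Background Information reports that, in complete clefts, the device reduced nostril width and raised nostril height. If treated infants are older at the final photograph, growth would tend to mask the first effect and exaggerate the second.

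The size is unknown, because the documents give no growth rate, SD or number of controls. On the assumptions shown, a 1-month mean gap implies a false-positive rate of about 6-12%. A reader might infer rates of 17-32%; those need a bias of 0.4-0.6 SD, which on the assumed growth rates means a mean gap of more than 1 month, and the printed ranges do not establish that.

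**What to change.** 1. Reconcile the title page, Study Design (Prospective), Study Population (Retrospective) and Study Procedures (Prospective) on treatment length, subject duration and timing of repair. Which figures apply is the sponsor's decision.
2. Record age at each photograph in both groups.
3. In Statistics, make the between-group comparison of change account for age at the final photograph or for the interval between photographs, and report the distribution of that variable by group.

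The first item is wording. The second uses dates that should already be in the record, since age is to be collected anyway. The third adds one model term, which costs some precision with 10 treated infants. If the age ranges of the two groups barely overlap, adjustment would rest on extrapolation; the distribution by group would show this.

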**Study Population**

Previous studies have examined similar number of patients and identified significant findings on presurgical infant orthopedic appliances[4, 5, 7]. To reduce the variability in this study, patient inclusion and exclusion criteria are strict.

**Retrospective:**

- The Texas Cleft-Craniofacial Team photo database will be queried for patients with incomplete unilateral cleft lip who have undergone cleft lip repair from 2015-2020.
  - Inclusion criteria
    - Unilateral cleft lip with or without cleft palate
    - Patients of a single surgeon ([name])
    - Patients with complete photographs: □ After birth, first visit

IRB NUMBER: HSC-DB-20-0311

- At cleft lip repair (3-4 months)
- Post-operative cleft repair (about 1 year of age)
  - Exclusion criteria
    - Bilateral cleft lip or complete unilateral cleft lip
    - Patients operated on by other primary surgeons
- Patients with incomplete photo records will be evaluated to determine if the patient should be excluded

**Prospective:**

- Patients will be approached at their first visit to the Texas Cleft-Craniofacial Team starting in 2020.
  - Inclusion Criteria:
    - Patients with incomplete unilateral cleft lip with or without cleft palate
    - Patients of any surgeon
    - Exclusion Criteria:
      - Patients with bilateral cleft lip or complete unilateral cleft lip
      - Patients whose parents refuse to consent to inclusion
      - Patients with tape allergies to the adhesive of the DynaCleft®
      - Patients with syndromic craniofacial conditions or Tessier type facial clefts

**Study Procedures**

**Retrospective:**

- Electronic health records of infants with unilateral incomplete cleft lip and/or palate who underwent or is undergoing surgery within the University of Texas Health Science Center will be reviewed. Patients whose clefts are associated with a syndrome will be excluded along with those that have had any other presurgical interventions. Qualifying participants must have had surgical repair after January 2015 or will have surgery before January 2021. Charts with incomplete patient data, inaccessible contact of caregiver, inadequate records or both pre- and post-op photographs in the necessary angles will be excluded.

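### Control charts are screened on post-operative photographs and caregiver contact that the primary comparison does not use, and the two-month device rule leaves the treated analysis set unclear

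*Combined protocol and SAP*

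**What the plan says.** **Photographs the primary comparison uses.** Outcome Measures sets two time points for all four primary measurements: the initial examination and surgery. Study Design, Retrospective, agrees: "Necessary photographs are to include those taken at the initial visit soon after birth and those at the visit immediately prior to lip surgery". Study Design, Prospective, asks for the same two sets from treated infants. No post-operative endpoint is defined anywhere.

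**Photographs and contact the control rules ask for.** Study Population, Retrospective, lists three items under complete photographs: the first visit, "At cleft lip repair (3-4 months") and "Post-operative cleft repair (about 1 year of age"). It then adds: "Patients with incomplete photo records will be evaluated to determine if the patient should be excluded". No criterion for that evaluation is given. Study Procedures, Retrospective, is stricter: "Charts with incomplete patient data, inaccessible contact of caregiver, inadequate records or both pre- and post-op photographs in the necessary angles will be excluded". The repair window is: "Qualifying participants must have had surgical repair after January 2015 or will have surgery before January 2021".

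**Treated group.** Study Procedures, Prospective, makes two months of device treatment before surgery a condition of qualifying. The prospective inclusion and exclusion criteria under Study Population do not contain this condition. The same Study Procedures text says that treatment duration and caregiver compliance will be recorded. Statistics names no analysis set.

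**The concern.** A control chart with both presurgical photograph sets supplies everything the primary comparison needs. Rejecting it for want of a later photograph, or because the caregiver cannot be reached, loses information for no gain in the primary analysis. The sections also differ on whether an incomplete record is excluded outright or considered individually. Two people pulling charts under this protocol could therefore assemble different control groups. In a non-randomised comparison, that discretion should be closed before any chart is measured.

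The 1-year photograph has a timing side too. The infants least likely to have one when charts are pulled are the most recent repairs. They are the controls closest in time to the treated group, for whom the plan says "Patients will be approached at their first visit to the Texas Cleft-Craniofacial Team starting in 2020".

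On the treated side, if the two-month condition acts after enrolment, the estimate describes infants who kept the device on rather than all who started it. Controls face no corresponding condition. With 10 infants planned, one or two such exclusions matter.

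**Working it through.** The plan states no control count, standard deviation, attrition rate or chart-pull date, and its 10 treated infants rest on feasibility and precedent. There is no plan figure to reproduce. Steps 2 to 4 use assumptions, named where they enter.

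**1. The sections side by side**

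| Section | Photographs asked of controls | Incomplete photo records | Caregiver contact |
|---|---|---|---|
| Outcome Measures | initial, surgery | not addressed | no |
| Study Design | presurgical only | not addressed | no |
| Study Design, Retrospective | initial, pre-surgery | excluded | no |
| Study Population, Retrospective | initial, at repair, about 1 year | judged case by case | no |
| Study Procedures, Retrospective | pre- and post-operative | excluded | yes |

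Read literally, the last rule excludes charts that have both pre- and post-operative photographs. The photograph list in Study Population shows that it must mean charts without them. Contact is not needed for consent, because Ethics plans a waiver for the retrospective part. Its plausible use is the quality-of-life survey.

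**2. Calendar effect of a 1-year photograph**

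Inputs: repair at 3-4 months (Study Population) and repairs from January 2015 to January 2021 (Study Procedures). Even accrual is assumed.
- Wait from repair to 1 year of age: 12 - 4 = 8 to 12 - 3 = 9 months.
- Chart pull in January 2021: the window is 72 months, so 8/72 = 11.1% to 9/72 = 12.5% of charts could not yet have the photograph.
- With repair at 6 months, the upper age in Study Design, Prospective: 6/72 = 8.3%.
- Last eligible repair, December 2020, plus 8-9 months gives August to September 2021. A pull after that loses none for this reason.

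**3. Precision lost when usable controls are dropped**

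The standard error of the group difference is proportional to sqrt(1/n1 + 1/n2), with n1 = 10 treated. The control counts are assumed.
- 30 to 26 controls: 0.372/0.365 = 1.02.
- 30 controls losing 25% (22.5 left): 1.04. Losing 50% (15 left): 0.408/0.365 = 1.12.
- 10 controls losing 25% (7.5 left): 1.08. Losing 50% (5 left): 0.548/0.447 = 1.22.

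**4. Two-month rule, only if it is an exclusion after enrolment**

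Let s be the share of starters who stop early but stay in the study, and f their change as a fraction of the completers' change. Completer mean / all-starter mean = 1/[(1 - s) + s × f]. Both s and f are assumed.

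| | f = 0 | f = 0.5 |
|---|---|---|
| s = 10% | 1/0.90 = 1.11 | 1/0.95 = 1.05 |
| s = 20% | 1/0.80 = 1.25 | 1/0.90 = 1.11 |

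Analysing 9 of 10 treated infants widens the standard error by 3-4%, and 8 of 10 by 6-9%, across 10 to 30 controls.

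**The case against.** The opposing case is that this is a wording inconsistency in a 10-infant pilot, and several of its points stand.

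- A reader might infer that Study Population itself throws out charts without a 1-year photograph. It does not: it sends incomplete records to review. Only Study Procedures excludes them, and only on its evident rather than literal meaning.
- A reader might infer that a substantial share of recent controls must be lost. That needs an early chart pull. The title block gives a two-year study duration. Counted from "Version Date: 07/16/2020", that runs to about July 2022, well past September 2021. A final pull at the version date would also sit badly with a rule that admits surgery still to come.
- A reader might blame the two-month rule for every early stopper. Data and Safety Monitoring lets families end participation for irritation, and Ethics discontinues participation for allergy. Those infants leave with or without the rule, which can remove only infants who stop the device yet stay in the study.
- The rule can be read as an entry condition: enough time must remain before surgery. The references to families who completed, in Purpose and Study Design, concern the quality-of-life survey, not the photograph endpoints.
- Statistics stops approaching families at the 10th enrolment and ends the trial when the 10th patient completes. Read in sequence, these can be the same patient, so this is at most a clarification and not evidence of a replacement conflict.

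Caregiver contact also has a possible purpose, since parents who decline the device may complete the survey. That justifies recording contact for the survey. It does not justify excluding a chart from the photograph comparison.

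**Conclusion.** The concern holds for the controls. The sections disagree on which charts are usable, and Study Procedures, followed on its evident meaning, discards infants who have every primary measurement. The supported harm is lost precision: about 2% on the standard error if 30 controls become 26, and 4-22% if 25-50% are lost from 30 or 10. All of these counts are assumed. The calendar loss of about 11-13% applies to a pull in January 2021, with even accrual and repair at 3-4 months. It disappears from about September 2021.

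It is tempting to go further and say that the filter biases the device effect or inflates the false-positive rate. The documents do not support that. Bias requires return for a photograph, or reachability, to be related to presurgical change, and nothing in the plan shows such a relation. Its direction and size cannot be obtained.

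The treated-group part is conditional. If the two-month rule excludes after enrolment, the completer mean would be about 1.05-1.25 times the all-starter mean under the assumed 10-20% stopping and none or half of the completers' change. If it is an entry rule, it removes nobody already enrolled. The plan should say which.

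**What to change.** 1. **Controls.** For the primary comparison, include every consecutive, otherwise eligible chart that has the two photograph sets named in Study Design, Retrospective. Remove the post-operative photograph and caregiver-contact conditions, and the case-by-case sentence, from Study Population and Study Procedures. Keep contact as a requirement for survey use only.
2. **Treated infants.** Define the primary analysis set as all infants who began DynaCleft, remain in the study and have a pre-surgery photograph, whatever their treatment duration. Report the two-month subset as a sensitivity analysis, using the duration and compliance data already to be recorded. State what qualifying means in Study Procedures, Prospective.
3. **Reporting.** Give withdrawals and exclusions by group and reason, including how many charts each control filter removes. A clarifying phrase in Statistics on whether 10 counts enrolled or completed infants would help.

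The cost is revised eligibility and analysis-set wording, a few more charts to measure, and a treated estimate that may be smaller because early stoppers are kept. Families who have withdrawn need not be approached for photographs, because the proposed set is limited to infants still in the study.
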